1. SUMMARY

Rationale: Physical activity is beneficial to older adults to improve health conditions and decrease risk on frailty. Coach2Move is a physiotherapeutic intervention aimed at maintaining or improving mobility among older adults who visit physiotherapists using a personalized tailored approach based on an in-depth hypothesis oriented behavioural, physical and environmental diagnostic exploration with a primary focus on a long-lasting increase of physical activity in daily living and enhancing self-efficacy and self-management using the social context combined with a physical training.

Our hypothesis is that implementing Coach2Move in physiotherapeutic practice leads to better physical outcomes and lower costs than usual care.

Objective: The main objective of this study is to research whether implementation of a focused personalized problem-oriented coaching intervention (Coach2Move strategy) is more effective to improve physical activity, mobility and health status in community-dwelling older adults than usual care physiotherapy. In addition, cost-effectiveness will be determined.

Study design: stepped wedge cluster randomised trial and mixed methods process analysis. Due to the design, control- and intervention period range from 3 to 15 months. The period of wash-out and implementation lasts 3 months.

Study population: Elderly people ≥ 70 years old referred to the physiotherapist because of a decrease in physical functioning/ mobility and/or at risk of physically inactive lifestyle.

Implementation: The Coach2Move approach is stepwise introduced in the participating practices. At a predefined randomised time point during the study, an implementation and wash-out period takes place in which the practices switch from control to intervention. This is preceded by an online e-learning in which two patient cases are being discussed. The implementation is conducted by a course consisting of two day parts in which the PT(G)'s are being educated in the aspects of Coach2Move. During the implementation and wash-out period, no measurements take place in the practices so the PT(G)'s have the time and opportunity to fully explore and experiment with the implementation of the Coach2Move strategy among their own clients. In addition to the course, three peer assessment meetings are being planned in which the PT(G)'s reflect and evaluate on their own use of Coach2Move and to those of others.

Intervention: The Coach2Move approach is stepwise implemented in 16 physiotherapy practices. On each site, at least one physiotherapist in geriatrics and one physiotherapist will receive a two-day training in the Coach2Move approach, which makes use of elements of the Hypothesis Oriented Approach for Clinicians (HOAC-II) and the International Classification of Functioning and Health (ICF). Participants receive physiotherapy according to the Coach2Move approach instead of the usual care physiotherapy.

Main study parameters/endpoints: In this study, each participant is measured four times. The first, being the baseline measurement (T0) is prior to physiotherapeutic treatment, while the second is directly after ending the treatment (T1). The following two are respectively six- (T2) and twelve months (T3) after the moment the participant started the treatment.

The primary outcome measures are the cost per quality-adjusted life year (QALY) gained, mobility measured by the modified Timed up and Go (TUG) and the level of moderate physical activity (LAPAQ). Secondary outcomes include: quality of life (EQ-5D), the degree of frailty (Evaluative Frailty Index for Physical activity), perceived effect (Global Perceived Effect and Patient Specific Complaints) and health care utilization costs.

In addition, qualitative data of experiences in implementation of Coach2Move will be gathered from interviews with patients and focus groups with PTG's and PTs.

The quantitative analysis will be based on quality indicators of medical records of patients for each physiotherapist scored by the researcher. The files in the control period are compared with those after implementation of Coach2Move.

Nature and extent of the burden and risks associated with participation, benefit and group relatedness: The physiotherapeutic process according to the Coach2Move strategy does not have more risk compared to usual care physiotherapy. The additional load related to the study participants are being exposed to consists of the three measurement moments in which questionnaires are being conducted. These moments each will take the patients approximately 60 minutes.

Since we believe that all older adults could benefit from the Coach2Move approach, we have composed broad in- and exclusion criteria so we would include a realistic sample of the Dutch older adults who are seeing a PT(G) for mobility problems. This includes older adults suffering from dementia, since we hypothesize we could involve informal caregivers or other health authorities in the treatment to help achieve the set goals.

2. INTRODUCTION AND RATIONALE

The population of older adults in the Netherlands is increasing. An increase of 1.4 million older adults is estimated between 2012 and 2041 [1]. Not only the number of older adults is increasing, the life expectancy is rising as well. Along with an increasing age, the need for healthcare is rising as well. Older adults are more vulnerable for adverse health outcomes such as functional dependency, hospitalisation and death [1].

A recent systematic review has shown that physical activity is beneficial for older adults to prevent or even reduce frailty and improve quality of life [2]. However, increasing physical activity is known to be very challenging; especially if an individual is coping with health disorders, ageing and unhealthy lifestyle [3]. Older adults with limited mobility reported poor health, fear of falling, negative experiences, lack of company and an unsuitable environment as barriers to exercise [4]. However, a sedentary lifestyle leads to more adverse outcomes [5]. Physicians and physiotherapists play a key and pivotal role in promoting exercise behaviour among older adults. Especially in the elderly population, the lack of knowledge and understanding of the relationship between moderate exercise activity and health is a relevant barrier, as many lived through a time period when exercise was not valued or deemed necessary. In addition, many elderly feel they already receive enough exercise in their activities of daily living [6].

A new and promising approach to help frail older adults to increase their levels of physical activity is Coach2Move. This strategy, based on clinical reasoning conform the Hypothesis Oriented Algorithm for Clinicians (HOAC-II) and the International Classification of Health (ICF), provides guidance in the diagnostic and therapeutic process to physiotherapists [7-9]. This is complemented with behavioural changing techniques such as motivational interviewing and shared decision-making, which are a valuable addition to usual physiotherapy[10]. By effectively using the context of the patient and focusing on strengths and the potential to adapt instead of the disease and the weaknesses, a high level of adherence to physical activity is expected to maintain. In a previous trial (CMO registration number: 2012/233), we demonstrated that the Coach2Move approach is superior to regular physiotherapy in terms of increasing physical activity, reducing frailty, improving quality of life and reducing healthcare costs [11]. In short, in less physiotherapeutic sessions, better outcomes were realized. It is therefore that the RIVM (Rijksinstituut voor Volksgezondheid en Milieu) has appraised the Coach2Move approach as good evidence for effectiveness.

Despite these promising findings, we still have questions regarding the generalisability of these findings. Our reservations towards the generalisability of the approach are caused by the following:

1. We included a modest (n=130), yet somewhat selective study sample: nearly half of the eligible individuals declined randomisation and thereby participation. We need to understand how this group of eligible non volunteers respond to Coach2Move. Therefore, we will use a study design that avoids randomisation at the patient level.
2. The Coach2Move approach significantly increased the level of moderate physical activity among the treatment group and reduced levels of frailty significantly after 6 months, but the clinical importance of these findings is still unclear. Thus, we need a replication of the effects in the light of physical functioning, a larger more variable study population and a longer follow-up.

In addition, the results from the earlier carried out RCT concerning the cost-effectiveness of Coach2Move have to be replicated on a larger scale.

For the reasons mentioned above, it is important to further implement Coach2Move and study its effect, costs, and feasibility in current practice. A stepped wedge cluster randomised trial design is chosen because we believe that the implementation strategy will do more good than harm (making a parallel design, in which certain practices do not receive the intervention or to withdraw the intervention as would occur in a cross-over design, is unethical) and it furthermore minimizes contamination.

To further improve the implementation of Coach2Move, process evaluation will be carried out by having several meetings in which both participants and PT(G)'s will be interviewed on their experiences and their opinions on Coach2Move. Data received by process evaluation will be analysed both quantitatively and qualitatively.

The objective of this study is to assess the cost-effectiveness of the implementation of a patient and context focused tailored coaching intervention (Coach2Move) in the daily physiotherapy practice for older adults with mobility problems compared to usual physiotherapy. Our hypothesis is that Coach2Move leads to better physical outcomes and lower costs than usual care.

3. OBJECTIVES

Primary Objective:

The aim of this study is to investigate the (cost)effectiveness of the implementation of Coach2Move physiotherapy of the management of community-dwelling older adults (≥ 70 years) with mobility problems and/or physically inactive lifestyles in a pragmatic real-world setting.

Our main research question is:

Can we improve cost-effectiveness of physiotherapy care for older adults with mobility limitations? In other words, does the implementation of the Coach2Move strategy lead to better outcomes and lower costs than usual care physiotherapy?

Secondary Objective(s):

By use of a process evaluation [12], we also aim to investigate the processes through which the Coach2Move intervention operates on outcomes and how the implementation of the program is achieved in the context of potential organisational and other differences between places and therapists.

Our secondary research questions are:

1. Which factors in the delivery procedures influence the reach of the intervention?
2. Which factors in the fidelity of the intervention influence the outcomes?
3. What are the patient experiences concerning effectiveness, pros and con's of the Coach2Move intervention?
4. What are the experiences of Physical Therapists (PT's) and Physical Therapists in Geriatrics (PTG's) concerning effectiveness and feasibility and which barriers and facilitators for implementation are perceived?
5. What are the experiences of relevant stakeholders in the multidisciplinary network concerning effectiveness and practicability of Coach2Move?

4. STUDY DESIGN

To assess the cost-effectiveness of Coach2Move compared to usual physiotherapy care, we will use a stepped wedge cluster randomised trial design. A stepped wedge study has several advantages over RCTs: it allows evaluating as well as implementing a new promising intervention (Coach2Move) versus regular care in real-life setting and minimizes nonparticipation and contamination.

In this study 16 physiotherapy practices will be included. The 16 practices will be divided into 4 clusters (4-4-4-4). Each practice will include at least 25 patient during the entire duration of the study, which means a minimum number of 400 (16x25) patients will be included. Per cluster four months are planned for implementation of Coach2Move, from which one month is incorporated to serve as a wash-out period between the control and implementation phase (thus resulting in 15 months of data in all practices) (please see Figure 1 for a visual depiction). During the wash-out and implementation period in a cluster, included patients will not be measured. In total, this should generate approximately 200 participants in the control group and 200 participants in the intervention group.

Control group is defined as all patients who meet the inclusion criteria and signed informed consent, who were treated in the indicated practices by participating therapists prior to the Coach2Move education of those therapists, whereas the intervention group is defined as all eligible patients who were treated after the Coach2Move education of the therapists. In other words, the control group receives regular physiotherapy, whereas the intervention group receives physiotherapy conform Coach2Move strategy.

For patients included during these 15 months, we will collect data at baseline, directly after the end of the program and 6 and 12 months after the start of intervention. In this stepped wedge study, we have set our measurement periods at time intervals of three months, resulting in a total inclusion duration of 15 months, an implementation period of 3 months and a follow-up of 12 months (thus clinical study duration 30 months in total). At the start of the study, all clusters start together in the control group, where none of the practices work according to the Coach2Move strategy and provide usual care. At different time points the clusters will cross-over to the intervention condition. The time points at which the different practices transition to Coach2Move are determined at random. By the end of the trial, all practices will have implemented Coach2Move.

The Implementation and Wash-out period consists of 3 months in which the therapists retrieve a 2-day education in Coach2Move and in which 3 peer assessment meetings take place. During this period, no measurements are carried out to give the therapists the opportunity to gain experience with Coach2Move before the measurements commence in the intervention period. This has no direct consequences for the participants.

All data will be collected by researchers from Radboudumc. Data sampled at baseline relevant for clinical decision-making will be communicated to the PT(G), to avoid load on the patient.

Figure 1. Depiction of proposed stepped wedge, cluster randomised design.

	3 months	6 months	9 months	12 months	15 months	18 months
Group 1 (Practices 1,2,3,4)	Control	Imp + WO	Intervention	Intervention	Intervention	Intervention
Group 2 (Practices 5,6,7,8)	Control	Control	Imp + WO	Intervention	Intervention	Intervention
Group 3 (Practices 9,10,11,12)	Control	Control	Control	Imp+ WO	Intervention	Intervention
Group 4 (Practices 13,14,15,16)	Control	Control	Control	Control	Imp+ WO	Intervention

Abbreviations: Imp +WO = Implementation and wash-out period.

A mixed methods process evaluation is designed to investigate the processes through which the Coach2Move intervention operates on outcomes and how the implementation of the program is achieved in the context of potential organisational and other differences between regions and practices.

Quantitative data will be collected and qualitative analyses (open interviews, focus groups and surveys) will be held with the participating PT(G)'s, relevant stakeholders and patients. Hindering and facilitating factors found during analysis will be used to fine-tune the implementation of the intervention strategy.

To test fidelity quality indicators are scored by reviewing patient files of physiotherapists.

This will be done by two independent blinded persons. Random sampling of patient files of different time periods after implementation will be compared with files from the control period. Subject to review is the change in scores between and after implementation of Coach2Move.

Time schedule:

July 2017 – October 2017	Development of implementation tools: educational materials, ICT optimization per practice, preparation measurement economic evaluation, development of measurement instruments for process evaluation, and randomisation of start points, meeting with the patient advising group to reflect on educational material and measurements. Publication of the trial protocol and the process analysis protocol.
November 2017 – March 2019	Gathering of data and measurements of actual usual care and care based on the Coach2Move approach and experiences with the implementation by professionals and patients.
November 2017 – March 2020	Control- and intervention measurements over 4 clusters: inclusion of patients, quality indicator measurement (clinical reasoning, patient-centeredness and monitoring by measurements), measurement of primary and secondary outcomes on pre-post and at 6- and 12 months follow-up.
March 2020 – December 2020	Finalizing analyses and publications.

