Another aspect of the study is to evaluate the fidelity of the PT(G)'s to Coach2Move. This is done by the scoring of quality indication scores of patient files. PT(G)'s are asked to assess patients conform the Coach2Move approach. This asks for an extensive and thorough intake to require optimal clinical reasoning during the therapeutic process.

By scoring the files on integrality of data, it can give insight in the diagnostic therapeutic process before and during the implementation of Coach2Move. Scoring will be independently carried out by two researchers. Of every participating therapist, 10 files will be scored: 5 during the control period and 5 during the implementation period.

b. Randomisation, blinding and treatment allocation

Coach2Move is rolled-out sequentially to 4 groups; each comprising 4 physiotherapy practices. The time points at which the different practices receive Coach2Move are determined at random.

Randomisation will be carried out by a random number generator operated by an external independent researcher. By the end of the trial, all practices will have implemented Coach2Move (Figure 1).

Blinding takes place at patient level. Although patients receive an information letter prior to participation, the exact goal of the study is not specified to make sure the expectations are not biased by placement in control- or intervention group. It is stated that the study focuses

on gaining a better understanding in physiotherapeutic treatment among older adults and therefore monitors health before- and after the treatment.

Since the Coach2Move strategy relies heavily on a more extensive and thorough intake including the usage of several questionnaires which otherwise would not be used with regular physiotherapy, it is therefore complicated to blind both the participants as well as the researchers since this study uses outcomes otherwise not obtained.

c. Study procedures

Participating subjects are tested on four occasions: prior to the intervention, after 3, 6 and 12 months after commencement of the intervention.

Subjects are exposed to several questionnaires on the four moments of testing. One physical test is carried out on each of these four moments.

Procedure of patients in the study:

1. Registration at physiotherapy practice
2. Information on study
3. Informed consent

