Data analysis to determine the overall effectiveness strategy subsequently involves comparison of the data points in the control section of the wedge with those in the intervention section. Because of the hierarchical design (patients nested within practices or within therapists), multilevel linear and logistic regression analysis will be used to compare the outcomes between treatment groups, with age, sex, comorbidity, frailty level and physical functioning at baseline at the patient level as covariates[13]. Time will be included as a fixed effect according to Donkers et al. [13]. In addition, subgroup analyses will be performed between PT and PTG levels.

c. Other study parameters

Qualitative Data Analysis

Interviews and focus group discussions will be elaborated verbatim (every word captured exactly, each final anonymised transcript will be added to the analysis). A structured thematic approach will be used to analyse the qualitative data.

The analysis will consist of five steps: 1) familiarization and initial coding line by line by two researchers; 2) developing a consolidated codebook; 3) coding and indexing all transcripts against the consolidated codebook, and discussion in the research group to focus on key findings for each study objective; 4) charting overall findings and look at any differences in patients, practices and context in dialogue with the project group and patient panel; 5) synthesis and drawing conclusions. In the analysis phase, descriptive summaries of interview data will be produced presenting the data per practice to help identify patterns.

Synthesizing quantitative and qualitative results:

An overall synthesis of the findings of the process evaluation study will take place to describe the context, the implementation of the intervention and the mechanisms of impact, with the aim of explicating the main trial findings and interrogating the intervention theory. Where data is available, we will test hypotheses based on qualitative analysis quantitatively. We will also, where appropriate, conduct the reverse operation and use quantitative data to focus qualitative analyses. Where data from different sources provide competing narratives or findings, we will make these explicit when reporting and provide a justification of our interpretation in such differences.

Budget Impact Analysis (BIA):

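### The only definition of the arms follows the actual education of therapists, not the practice's randomised step, so late or missed training would make the comparison partly non-randomised

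*Combined protocol and SAP*

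**What the plan says.** Section 4 (Study design) holds the only explicit definition of the two groups. Control patients are those "who were treated in the indicated practices by participating therapists prior to the Coach2Move education of those therapists"; "the intervention group is defined as all eligible patients who were treated after the Coach2Move education of the therapists". Both halves turn on an event that happens to therapists.

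Randomisation works at another level. Section 4 states: "The time points at which the different practices transition to Coach2Move are determined at random". Section 8.b repeats it: "The time points at which the different practices receive Coach2Move are determined at random". Figure 1 shows the schedule by groups of practices.

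The effectiveness analysis in section 9.b is a "comparison of the data points in the control section of the wedge with those in the intervention section". It does not say what places a patient in one section or the other. It also speaks of treatment groups, which only section 4 defines. Neither section contains an intention-to-treat statement.

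Two further statements bear on how often the rules could diverge. Section 1 (Intervention) says that on each site "at least one physiotherapist in geriatrics and one physiotherapist will receive a two-day training". Section 4 puts the education inside an unmeasured block: "The Implementation and Wash-out period consists of 3 months in which the therapists retrieve a 2-day education in Coach2Move", and "During the wash-out and implementation period in a cluster, included patients will not be measured". Elsewhere section 4 gives the length of this block as four months, one of them for wash-out.

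**The concern.** The randomised quantity is the calendar time of a practice's switch. A comparison keeps the protection of randomisation only if patients are classified by that time. The section 4 definition classifies them by when training actually took place, which is known only after randomisation and may depend on the therapist.

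Consider a practice past its scheduled block in which one enrolled therapist was educated a period late. Read literally, section 4 makes that therapist's patients control, while colleagues' patients in the same practice and months are intervention. For a therapist who is never trained, or who joins after the step, the wording is unclear: the patients could be control, or belong to neither arm because the therapist is not a participating one. In each case patients are sorted after randomisation by a therapist characteristic. If therapists who train late or not at all differ in experience, motivation or caseload, that difference enters the estimated effect.

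It also bears on the question asked. Section 3 sets out to estimate the effect of implementing Coach2Move in a pragmatic, real-world setting. Incomplete or delayed training is part of implementation.

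**Working it through.** **Inputs from the documents.** Figure 1 in section 4: 4 groups of 4 practices, 6 periods, implementation cell empty. Section 6.d: 5 patients per practice in each of 5 measured periods (400 in total), ICC 0.10, SE 0.21 × SD; TUG effect 1.4 s, SD 2.0 s, margin 0.4 s; LAPAQ effect 15 min, SD 30 min, margin 5 min; correlation of the two estimates at most +0.3; power 86%.

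**Assumptions, because the documents give no figures.** A share f of 10%, 20% or 30% of each practice's patients is seen by affected therapists; their outcomes are d = 0.2 or 0.3 SD worse in all periods; the true effect is zero; practice random intercept only, no covariates; one-sided 0.025 for each test, since section 6.d states no alpha.

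**Step 1: reproduce the plan's figures.** With outcome variance 1, the covariance within a practice is V = 0.90·I + 0.10·J. The estimate is (Σ X′V⁻¹X)⁻¹ Σ X′V⁻¹y, with period effects and one intervention term in X. This gives 200 control and 200 intervention patients and an SE of 0.213 SD (plan: 0.21).

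Power is P(TUG superior and LAPAQ non-inferior) + P(LAPAQ superior and TUG non-inferior) − P(both events), from a bivariate normal with SEs 0.21 × 2.0 = 0.42 s and 0.21 × 30 = 6.3 min. At correlation +0.3 this is 85.8% (plan: 86%). Both figures reproduce.

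**Step 2: expected estimate under each way of classifying**, true effect zero, in SD units:

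| Classification of affected therapists' patients | d = 0.2; f = 10/20/30% | d = 0.3; f = 10/20/30% |
|---|---|---|
| By the practice's randomised step | 0 / 0 / 0 | 0 / 0 / 0 |
| Left out before and after the step | 0 / 0 / 0 | 0 / 0 / 0 |
| Counted before the step, left out after it | 0.02 / 0.04 / 0.06 | 0.03 / 0.06 / 0.09 |
| Control for one period after the block, then intervention | 0.06 / 0.10 / 0.12 | 0.09 / 0.15 / 0.17 |
| Control throughout | 0.11 / 0.14 / 0.16 | 0.16 / 0.22 / 0.24 |

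The third row is simply f × d. With d = 0 every entry is zero, and with f = 0 the rules coincide.

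**Step 3: size on the endpoint scales.** The largest entry, 0.24 SD, is 0.24 × 2.0 = 0.48 s on TUG and 0.24 × 30 = 7.2 min on LAPAQ. The relevant effects are 1.4/2.0 = 0.7 SD and 15/30 = 0.5 SD.

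**Step 4: effect on the SE and the error rate.** With f = 10% coded control throughout, the model SE falls from 0.213 to 0.163 SD, because contrasts between therapists within the same practice and period, which nobody randomised, now add information. With d = 0.2 the one-sided type I error for one endpoint is P(Z > 1.96 − 0.106/0.163) = 9.5%, against 2.5%. In the one-period-late case it is P(Z > 1.96 − 0.062/0.196) = 5.0%.

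**Step 5: cost of classifying by step.** If a share f of post-step patients sees an untrained therapist, both effects shrink by the factor (1 − f). At f = 10% they are 1.26 s and 13.5 min. Power is 82%, 78%, 68% and 56% for f = 5%, 10%, 20% and 30%.

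**The case against.** The strongest reply is that the plan can be read as classifying by step already. Figure 1 and section 8.b describe a practice-level schedule, section 9.b compares sections of the wedge, and the section 4 wording may only be a plain description of the two conditions. A reader might infer that the sponsor has chosen an as-treated analysis and given up randomisation. The documents do not establish that. What stands is that the one explicit definition points to actual education, and nothing elsewhere overrides it.

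A reader might also infer that every untrained or replacement therapist's patients become control. Section 4 does not say so. Someone never educated has no time before education, and a late joiner may not be a participating therapist. Only late education of an enrolled therapist clearly fits the wording, which is why the last row of the table is the adverse end of a range.

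The unmeasured block absorbs delays that stay inside it. It does not absorb missed training, longer delays or later staff changes. The promise to train at least two therapists per site is a minimum, not evidence that training will slip.

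The calculation also omits the planned covariates and possible nesting within therapists (section 9.b). With d = 0.3, splitting the ICC equally between practice and therapist lowers the last row to 0.14/0.17/0.19 SD; placing it all at therapist level gives 0.12/0.14/0.15. Baseline adjustment may lower it further. Neither restores randomisation.

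Finally, the direction is assumed. If affected patients had the better prognosis, the bias would run against Coach2Move.

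**Conclusion.** The point holds as a conditional weakness in how the arms are defined. If all education takes place inside the unmeasured block, and therapists neither miss it nor join later, both rules classify every measured patient alike and nothing changes. If training slips past the block, the section 4 definition yields a contrast that is no longer purely randomised.

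Under the assumed shares and prognosis gaps the bias is about 0.02-0.09 SD if affected patients are left out after the step, 0.06-0.17 SD if they are one period late, and 0.11-0.24 SD if they are coded control throughout. At the upper end this slightly exceeds the planned SE of 0.21 SD. The ranges show what the wording permits; they do not forecast what will happen.

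It does not follow that the sample size is wrong. The stated 86% power reproduces and is unaffected by this point as long as training runs to schedule. The change should be made because it settles the primary classification before data are seen and needs only new wording.

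**What to change.** In sections 4 and 9.b, define the arm for the primary analysis by the practice's randomised step and the patient's T0 date. T0 before the practice's scheduled implementation block is control; T0 after it is intervention. This should apply regardless of when, or whether, the treating therapist was trained, and so cover late, never-trained and replacement therapists explicitly.

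Record each therapist's actual education date and use it only in a sensitivity analysis.

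Reconcile the three- and four-month lengths given for the block in section 4, since its start and end become the boundary between the arms.

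The cost is a change of wording plus the recording of education dates. The statistical downside is the dilution in step 5, for example power of about 78% instead of 86% at 10%. That diluted effect is the effect of implementation that the trial sets out to estimate.
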